5.4 Other restrictions

Not applicable.

6 Treatment

6.1 Study treatment

Details on the requirements for storage and management of study treatment, and instructions to be followed for subject numbering, prescribing/dispensing and taking study treatment are outlined in the Site Operations Manual.

6.1.1 Investigational treatment and control drug(s)

Table 6-1 Overview of study medication

Study drug name	Formulation	Appearance	Unit dose	Packaging	Provided by
LML134	Capsule	Corporate Confidential Information		Open label bulk	Novartis
Placebo	Capsule	Corporate Confidential Information		Open label bulk	Novartis

6.1.2 Additional study treatment

No additional treatment beyond investigational drug and control drug are included in this trial.

6.2 Treatment arms

Study treatments are defined as:

- A: single dose of LML134, on each of two consecutive nights
- B: single dose of placebo to LML134, on each of two consecutive nights

Subjects will be randomized to one of the following 2 treatment sequences in the ratio of 1:1.

Table 6-2 Definition of treatment sequences

Sequence	Period 1	Period 2
1	A	B
2	B	A

6.3 Treatment assignment and randomization

Randomized treatment will be assigned to individual subjects by way of a randomization number, which will be in the range of 5101-5146.

The randomization number is only used to identify which treatment the subjects have been randomized to receive. The Subject number assigned to a subject at Screening remains the unique identifier for the subject throughout the study. For information on subject numbering, please see ‘Subject numbering’ section in the SOM.

Replacement randomization numbers will be in the range of 6101-6146. If a subject requires a replacement, the replacement subject will be assigned a randomization number corresponding to the original subject (e.g. Subject 6103 would replace Subject 5103). Any additional subjects enrolled will use sequential subject numbering.

[Table 6-3](#) details the general details of the numbering of the subjects once randomized to treatment.

The randomization numbers will be generated using the following procedure to ensure that treatment assignment is unbiased and concealed from subjects and investigator staff. A randomization list will be produced by or under the responsibility of Novartis Drug Supply Management using a validated system that automates the random assignment of treatment arms to randomization numbers in the specified ratio. The randomization scheme for subjects will be reviewed and approved by a member of the Randomization Office.

Subjects will be randomized within the electronic NIRT system. Follow the details outlined in the Site Operations Manual regarding the process and timing of treatment assignment and randomization of subjects.

Table 6-3 Treatment Assignment Numbering

Cohort	Randomization numbers	Replacement randomization numbers
I (n = 46)	5101 - 5146	6101 - 6146

6.4 Treatment blinding

This is a subject- and investigator-blinded study. Subjects and investigators will remain blinded to study treatment throughout the study, except where indicated below.

The identity of the treatments will be concealed by the use of study drugs that are all identical in packaging, labeling, schedule of administration, appearance, and odor.

Site staff

With the exception of any unblinded site staff identified below, all site staff (including study investigator and study nurse) will be blinded to study treatment throughout the study.

Unblinding a single subject at site for safety reasons (necessary for subject management) will occur via an emergency system in place at the site (see [Section 6.7](#)).

Drug product will be supplied in bulk, so an unblinded pharmacist who is independent of the study team will be required in order to maintain the blind. This unblinded pharmacist will receive a randomization list or treatment allocation cards from Drug Supply Management with the appropriate treatment allocation numbers. Appropriate measures must be taken by the unblinded pharmacist to ensure that the treatment assignments are concealed from the rest of the site staff.

Sponsor staff

The following unblinded sponsor roles are required for this study:

- Unblinded field monitor(s)
- Unblinded sample analyst(s) (PK)

The unblinded field monitors are required to review drug accountability and allocation at site. The unblinded monitors are not provided with a randomization list directly but will be unblinded through review of source documentation compiled by the unblinded pharmacist, which details treatment allocation to individual subjects. The unblinded monitors will also be able to review the treatment allocation cards/randomization list provided to the unblinded pharmacist. The names of the unblinded monitor(s) are detailed in the Monitoring Plan.

The sample analysts will receive a copy of the randomization schedule (via request to the Randomization Office), to facilitate analysis of the samples. The sample analysts will provide the sample data to the study team under blinded conditions unless otherwise allowed.

The study statistician will be able to access the randomization list for interim analyses and is allowed to share unblinded information with the rest of the clinical team as appropriate for internal decision purposes, as outlined in [Table 6-4](#). For example, unblinded summaries and unblinded individual data can be shared with the team for interim analyses.

Study programmers and other personnel involved in study data analysis (e.g. biomarker expert) are allowed to access treatment assignment information for the purpose of conducting interim analyses.

The clinical trial team is allowed to share unblinded results with other sponsor staff (e.g. decision boards) as required for internal decision making on the study or the project at the time of interim analyses while the study is ongoing.

All unblinded personnel will otherwise keep randomization lists and data or information that could unblind other study team members confidential and secure except as described above.

Following final database lock all roles may be considered unblinded.

Table 6-4 Blinding and unblinding plan

Role	Time or Event			
	Randomization list generated	Treatment allocation & dosing	Safety event (single subject unblinded)	Interim Analysis & dose escalation
Subjects/Patients	B	B	UI	B
Site staff	B	B	UI	B
Unblinded site staff (see text for details)	B	UI	UI	UI
Drug Supply and Randomization Office	UI	UI	UI	UI
Unblinded sponsor staff (see text for details)	B	UI	UI	UI
Statistician/statistical programmer/data analysts	B	B	UI	UI
Independent committees used for assessing interim results	NA	NA	NA	NA
All other sponsor staff not identified above	B	B	UI	UG

B Remains blinded

NA Not applicable

UI Allowed to be unblinded on individual patient level

UG Allowed to be unblinded on treatment group level

6.5 Treating the subject

LML134 will be administered to the subject orally at the study site once a day in the evening.

LML134 and Placebo will be provided as capsules. Corporate Confidential Information

See the Site Operations Manual for further details.

Sponsor qualified medical personnel will be readily available to advise on trial related medical questions or problems.

6.6 Permitted dose adjustments and interruptions of study treatment

Study treatment dose adjustments and/or interruptions are not permitted.

6.7 Emergency breaking of assigned treatment code

Emergency unblinding must only be undertaken when it is essential to treat the subject safely and efficaciously. Most often, study treatment discontinuation and knowledge of the possible treatment assignments are sufficient to treat a study subject who presents with an emergency condition.

Emergency treatment code breaks are performed using the NIRT system. When the investigator contacts the system to break a treatment code for a subject, he/she must provide the requested subject identifying information and confirm the necessity to break the treatment code for the subject. The investigator will then receive details of the investigational drug treatment for the specified subject and a fax or email confirming this information. The investigator must also immediately inform the study monitor that the code has been broken.

In addition, the investigator must provide oral and written information to inform the subject how to contact his/her backup in cases of emergency when he/she is unavailable to ensure that un-blinding can be performed at any time.

An assessment will be done by the appropriate site personnel and sponsor after an emergency unblinding to assess whether or not study treatment should be discontinued for a given subject.

6.8 Treatment exposure and compliance

Pharmacokinetic parameters (measures of treatment exposure) will be determined in all subjects treated with LML134, as detailed in [Section 8.7](#).

The investigator must promote compliance by instructing the subject to take the study treatment exactly as prescribed and by stating that compliance is necessary for the subject's safety and the validity of the study. The subject must also be instructed to contact the investigator if he/she is unable for any reason to take the study treatment as prescribed.

6.9 Recommended treatment of adverse events

There is no specific antidote to LML134. Any adverse events should be managed symptomatically according to standard of care and applicable clinical guidelines.

In case of insomnia, non-pharmacological treatments should be attempted first.

6.10 Rescue medication

Not applicable.

6.11 Concomitant treatment

The investigator must instruct the subject to notify the study site about any new medications he/she takes or any change in dose of known medication after the subject was enrolled into the study and until the study completion.

All medications, vaccinations, over-the-counter drugs and significant non-drug therapies (including physical therapy, light therapy and blood transfusions) administered or taken within the timeframe defined in the entry criteria and prohibited medication sections until Study Completion, must be reported in the CRF on the Concomitant medications/Significant non-drug therapies page after the start of the study.

Medication entries should be specific to trade name, the route of administration, the start and discontinuation date, and the reason for therapy.

Each concomitant drug must be individually assessed against all exclusion criteria/prohibited medication. If in doubt, the investigator should contact Novartis before randomizing a subject or, if the subject is already enrolled, to determine if the subject should continue participation in the study.

7 Study completion and discontinuation

7.1 Study completion and post-study treatment

Each subject will be required to complete the study in its entirety and thereafter no further study treatment will be made available to them.

Study completion is defined as when the last subject completes their Study Completion visit, and any repeat assessments associated with this visit have been documented and followed-up appropriately by the Investigator, or in the event of an early study termination decision, the date of that decision.

All randomized and/or treated subjects should have a safety follow-up call conducted 30 days after last administration of study treatment. The information collected is kept as source documentation. All SAEs reported during this time period must be reported as described in [Section 9.2](#) and the Site Operations Manual. Documentation of attempts to contact the subject should be recorded in the source documentation.

7.2 Discontinuation of study treatment

Discontinuation of study treatment for a subject occurs when study treatment is stopped earlier than the protocol planned duration. Discontinuation of study treatment can be decided by either the subject or the investigator.

Study treatment must be discontinued under the following circumstances:

- Subject decision - subjects may choose to discontinue study treatment for any reason at any time.
- The investigator believes that continuation would negatively impact the safety of the subject or the risk/benefit ratio of trial participation.
- Any protocol deviation that results in a significant risk to the subject's safety or loss of significant data.
- Any occurrence of protocol exclusion criteria #6, #13, #19, #20, at the second Baseline visit.
- Pregnancy (see [Section 8.6](#) (Safety) and [Section 9.6](#) (Pregnancy reporting))
- Use of prohibited treatment as described in the relevant section
- Emergence of the following adverse events:
 - An SAE (including seizure) that is suspected to be related to study drug
 - An AE which is severe and suspected to be related to study drug
 - Infection of clinical concern, independent of the nature of the infection
 - Hyperthyroidism, evidenced by symptoms consistent with the clinical manifestation of the disease and confirmed by lab results of thyroid hormone levels

- Any impairment or blurring of vision or other visual complaints that might suggest retinal damage (e.g. curtain like shadow in the visual field, seeing sparks or flashes of light, appearance of many floaters, etc)
- Any significant change in behavior of the subject (e.g. signs of confusion, agitation or other symptoms indicating emerging psychiatric problems)
- Liver events, as defined in [Table 15-2-Appendix 1](#) of the protocol
- Renal events, as defined in [Table 16-1 Appendix 2](#) of the protocol
- Any of the following laboratory abnormalities:
 - Total white blood cell count <2000 cells/mm; <2.0 x 10⁹ /L
 - Hgb <8.0 g/dL; <4.9 mmol/L; <80 g/L
 - Any other laboratory abnormalities that in the judgment of the investigator, taking into consideration the subject's overall status, prevents the subject from continuing participation in the study.
- The following deviations from the prescribed dose regimen for the study drug
 - One or more missed doses
 - Dose of study drug was different from that specified in the study protocol

The appropriate personnel from the site and Novartis will assess whether investigational drug treatment should be discontinued for any subject whose treatment code has been broken inadvertently for any reason.

If discontinuation of study treatment occurs, investigator must determine the primary reason for the subject's premature discontinuation of study treatment.

Subjects who discontinue study treatment or who decide they do not wish to participate in the study further should NOT be considered withdrawn from the study UNLESS they withdraw their consent (see [Section 7.3](#), Withdrawal of informed consent). Where possible EOS assessments should be completed before they leave the sleep laboratory and they should be requested to return within 7 to 14 days to complete the follow-up visit. If they fail to return for future visits for unknown reasons, every effort (e.g. telephone, e-mail, letter) should be made to contact the subject/pre-designated contact as specified in [Section 7.4](#). (Lost to follow-up). This contact should preferably be done according to the study visit schedule,

After study treatment discontinuation, at a minimum, in abbreviated visits, the following data should be collected at clinic visits or via telephone/email contact:

- new / concomitant treatments
- adverse events/Serious Adverse Events

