9.3 Liver safety monitoring

To ensure subject safety and enhance reliability in determining the hepatotoxic potential of an investigational drug, a standardized process for identification, monitoring and evaluation of liver events has to be followed.

Please refer to [Table 15-1-Appendix 1](#) for complete definitions of liver events.

Follow-up of liver events

Every liver event defined in [Table 15-1-Appendix 1](#) should be followed up by the investigator or designated personnel at the trial site, as summarized below. Additional details on actions required in case of liver events are outlined in [Table 15-2-Appendix 1](#).

- Repeating liver chemistry tests (ALT, AST, TBL, PT/INR, ALP and G-GT) to confirm elevation within 48-72 hours.

These liver chemistry repeats should always be performed using the central laboratory, with the results provided via the standard electronic transfer. If results will not be available from the central laboratory within 24 hours, then the repeats can also be performed at a local laboratory to monitor the safety of the subject. If a liver event is subsequently reported, any local liver chemistry tests previously conducted that are associated with this event should have results reported on the unscheduled local laboratory CRF.

- If the initial elevation is confirmed, close observation of the subject will be initiated, including consideration of treatment interruption if deemed appropriate.
- Discontinuation of the investigational drug (refer to [Section 7.2](#) (Discontinuation of study treatment), if appropriate
- Hospitalization of the subject if appropriate
- Causality assessment of the liver event
- Thorough follow-up of the liver event should include

- Repeating liver chemistry tests two or three times weekly. Testing should include ALT, AST, ALP, PT/INR, and GGT. If total bilirubin is elevated $> 2 \times$ ULN, fractionation into direct and indirect bilirubin is required. To rule out muscular origin of transaminase elevations, CPK should be measured along with liver chemistry tests. Frequency of retesting can decrease to once a week or less if abnormalities stabilize or the study drug has been discontinued and the subject is asymptomatic. Retesting should be continued up to resolution.
- Obtaining a more detailed history of symptoms and prior or concurrent diseases.

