
15 Appendix 1: Liver Event Definitions and Follow-up Requirements

Table 15-1 Liver Event Definitions

Definition	Thresholds
Potential Hy's law cases	
 ALT or AST > 3 × ULN and TBL > 2 × ULN without initial increase in ALP to > 2 × ULN
ALT or AST elevation with coagulopathy	
 ALT or AST > 3 × ULN and INR > 1.5 (in the absence of anticoagulation)
ALT or AST elevation accompanied by symptoms	
 ALT or AST > 3 × ULN accompanied by (general) malaise, fatigue, abdominal pain, nausea, or vomiting, or rash, or eosinophilia
Isolated ALT or AST elevation	
 ALT or AST > 8 × ULN 5 × ULN < ALT/AST ≤ 8 × ULN 3 × ULN < ALT/AST ≤ 5 × ULN
Isolated ALP elevation	
 ALP > 2 × ULN (in the absence of known bone pathology)
Others	
 Any clinical event of jaundice (or equivalent term) Any adverse event potentially indicative of liver toxicity

Table 15-2 Actions required for Liver Events

Criteria	Actions required
Potential Hy's Law case ALT or AST elevation with coagulopathy ALT or AST elevation accompanied by symptoms Isolated ALT or AST elevation > 8 × ULN Jaundice	
 Discontinue the study treatment immediately Hospitalize, if clinically appropriate Establish causality Complete CRFs per liver event guidance*
Isolated ALT or AST elevation > 5 to ≤ 8 × ULN	
 If confirmed, consider interruption or discontinuation of study drug If elevation persists for more than 2 weeks, discontinue the study drug Establish causality Complete CRFs per liver event guidance*
Isolated ALT or AST elevation > 3 to ≤ 5 × ULN (patient is asymptomatic)	
 Monitor liver chemistry tests two or three times weekly
Isolated ALP elevation	
 Repeat liver chemistry tests within 48-72 hours If elevation is confirmed, measure fractionated ALP; if >50% is of liver origin, establish hepatic causality Complete CRFs per liver event guidance*

Criteria	Actions required

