Protein-creatinine or albumin-creatinine ratio increase \geq 2-fold or new onset dipstick proteinuria \geq 1+ or Albumin-creatinine ratio (ACR) \geq 30 mg/g or \geq 3 mg/mmol; or Protein-creatinine ratio (PCR) \geq 150 mg/g or >15 mg/mmol	
 Consider causes and possible interventions Assess serum albumin & serum protein Repeat assessment to confirm Consider drug interruption or discontinuation unless other causes are diagnosed and corrected
New onset glucosuria on urine dipstick (unless related to concomitant treatment, diabetes)	
Assess & document:
 
 Blood glucose (fasting) Serum creatinine Urine albumin-creatinine ratio
New hematuria on dipstick	
Assess & document:
 
 Urine sediment microscopy Assess sCr and urine albumin-creatinine ratio Exclude infection, trauma, bleeding from the distal urinary tract/bladder, menstruation Consider bleeding disorder

Additional specialized assessments are available to assess renal function or renal pathology. (Note: In exceptional cases when a nephrologist considers a renal biopsy, it is strongly recommended to make specimen slides available for evaluation by Novartis to potentially identify project-wide patterns of nephrotoxicity.)

Whenever a renal event is identified, a detailed subject history and examination are indicated to identify, document and potentially eliminate risk factors that may have initiated or contributed to the event:

- Blood pressure assessment (after 5 min rest, with an appropriate cuff size)
- Signs and symptoms such as fever, headache, shortness of breath, back or abdominal pain, dysuria, hematuria, dependent or periorbital edema
- Changes in blood pressure, body weight, fluid intake, voiding pattern, or urine output
- Concomitant events or procedures such as trauma, surgical procedures, cardiac or hepatic failure, contrast media or other known nephrotoxin administration, or other potential causes of renal dysfunction, e.g., dehydration, hemorrhage, tumor lysis

Table 16-2 Follow-up of renal events

Action	Follow up

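### Section 7.2 requires discontinuation for liver and renal events without naming table rows, yet 9 of the 10 rows it cites ask for less, and 4 of those 9 offer an interruption that Section 6.6 bars

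*Protocol*

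**What the plan says.** Protocol Section 7.2 introduces its list with "Study treatment must be discontinued under the following circumstances". Two of the bullets are "Liver events, as defined in [Table 15-2-Appendix 1](#) of the protocol" and "Renal events, as defined in [Table 16-1 Appendix 2](#) of the protocol". A later bullet in the same list makes one or more missed doses a reason to discontinue.

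The two tables cited are graded. In Appendix 1, Table 15-2, the row for isolated ALT/AST >3 to ≤5 × ULN says "Monitor liver chemistry tests two or three times weekly". In Appendix 2, Table 16-1, the response to new dipstick hematuria is a work-up that includes "Exclude infection, trauma, bleeding from the distal urinary tract/bladder, menstruation". The rows for a creatinine rise above 50% and for proteinuria or raised PCR/ACR say "Consider drug interruption or discontinuation unless other causes are diagnosed and corrected".

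Section 6.6 says "Study treatment dose adjustments and/or interruptions are not permitted" and gives no exception. Section 9.3 describes close observation after a confirmed liver elevation, "including consideration of treatment interruption if deemed appropriate". It then lists discontinuation, where appropriate, with a reference back to Section 7.2. Section 9.3 also places the definitions of liver events in Table 15-1, whereas Section 7.2 cites Table 15-2, the table of actions.

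**The concern.** A stopping rule contradicts the tables on which it relies. An investigator holding a creatinine rise of 25–49%, for example, finds mandatory discontinuation in Section 7.2 and a follow-up instruction in Table 16-1. Two sites could act in opposite ways on the same result, and each could point to protocol text in support.

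This matters for the analysis because the trial is a 2x2 crossover. The assessment schedule places chemistry and urinalysis at Screening, the Baselines, EOS/ET and Follow-up. A Period 1 alert found on scheduled tests therefore surfaces after both Period 1 doses and before Period 2. The conflicting text then governs whether the subject is dosed again. Protocol Section 11.4.2 bases the primary analysis on subjects with MSLT data from both periods, so a subject stopped at that point gives no within-subject comparison.

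**Working it through.** No sample-size, power or error-rate figure is involved. The check is a row-by-row comparison of the two action tables with Sections 7.2 and 6.6.

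| Table and row | Action in the table (paraphrased) | Immediate discontinuation required? | Interruption offered? |
|---|---|---|---|
| 15-2, row 1: potential Hy's law, coagulopathy, symptoms, ALT/AST >8 × ULN, jaundice | stop at once | Yes | No |
| 15-2, row 2: isolated ALT/AST >5 to ≤8 × ULN | discretionary once confirmed; stop if it lasts more than 2 weeks | No (conditional) | Yes |
| 15-2, row 3: isolated ALT/AST >3 to ≤5 × ULN | monitor | No | No |
| 15-2, row 4: isolated ALP | repeat test, look for hepatic cause | No | No |
| 15-2, row 5: AE suggesting liver toxicity | discretionary | No | Yes |
| 16-1, row 1: creatinine +25–49% | look for causes, follow up | No | No |
| 16-1, row 2: creatinine >50% | discretionary | No | Yes |
| 16-1, row 3: PCR/ACR or proteinuria | discretionary | No | Yes |
| 16-1, row 4: new glucosuria | assess and record | No | No |
| 16-1, row 5: new hematuria | assess and record | No | No |

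**Section 7.2 against the tables.** Rows: 5 + 5 = 10. Rows requiring immediate discontinuation: 1 + 0 = 1. Rows asking for less: 4 + 5 = 9. The first liver row pools five criteria. Counting criteria instead of rows, with each renal row as one, gives 5 + 4 + 5 = 14, of which 5 require immediate discontinuation and 9 do not.

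**Section 6.6 against the tables.** Interruption is offered in 2 liver rows and 2 renal rows, 4 of the 9. Three of these are triggered by a laboratory result and one by an adverse event. Section 9.3 offers it as well. The other 5 milder rows do not mention interruption and conflict with Section 7.2 only. The missed-dose bullet in 7.2 adds to the difficulty: with two doses per period, withholding the second appears to be a missed dose, which itself requires discontinuation.

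**Is there a reading of 7.2 that fits the tables?** Suppose it means that treatment stops where the cited table says to stop. For liver events this works: row 1 applies, and row 2 applies when the elevation persists. For renal events it leaves the bullet with no content, since Table 16-1 has 0 of 5 rows requiring discontinuation.

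**Effect on the data.** Each subject stopped between periods removes one paired comparison out of the 36 evaluable subjects planned in Section 11.7, that is 1/36 = 2.8%. The documents give no expected frequency for any alert, so the number of such subjects cannot be calculated.

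**The case against.** The strongest reply has five parts.

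- **The liver bullet may be narrower than it looks.** It cites the action table, and Section 9.3 qualifies discontinuation while pointing to 7.2. Together these can mean that only the rows whose action is discontinuation count. This is plausible, but 7.2 does not say so, and the reading cannot rescue the renal bullet.
- **Three incompatible instructions for one result.** A reader might infer this. The documents do not support it. Sections 7.2 and 6.6 agree with each other. The 4 rows that mention interruption offer discontinuation as the alternative, so discontinuing satisfies all three texts. The other 5 milder rows face only two texts.
- **Incidental dipstick findings must end treatment.** A reader might infer this too, but it is not certain. The liver and renal bullets may belong under the preceding adverse-event heading of 7.2, since the layout is unclear in the extracted text. Section 9.1 counts an abnormal laboratory value as an adverse event only if it causes signs or symptoms, is clinically significant or needs therapy. That would narrow the trigger. An event that did qualify would still meet a mandatory rule in 7.2 and a milder one in the table.
- **The interruption conflict has limited reach for scheduled tests.** Between periods no dose is due, and the wash-out may run to 5 weeks. Deferring Period 2 within that window is not plainly an interruption or a missed dose. This stands. The conflict remains for adverse events or unscheduled tests arising between the two doses of a period.
- **Other safeguards exist.** Section 7.2 separately requires stopping when the investigator sees a safety risk, and Section 8.6.4 requires clinically relevant deviations to be discussed with the sponsor. Section 11.7 allows extra enrollment if fewer than 36 subjects are evaluable. These reduce the harm but do not tell a site which text governs.

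**Conclusion.** The point holds in a limited form. Section 7.2 is unrestricted where 9 of the 10 rows it cites prescribe less than immediate discontinuation, one of them with a conditional stop after 2 weeks. For renal events no reading reconciles the bullet with its table. For liver events a narrower reading is available but unstated. As a separate matter, 4 rows and Section 9.3 offer an option that Section 6.6 excludes.

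The 9 of 10 describes the text; it does not measure lost data. The statistical consequence runs through entry to Period 2 and rests on alerts being found at the scheduled visits. Its size is unknown. The 18 completers reported in SAP Section 1.4 follow from a business decision to terminate, and nothing in the documents links that number to these rules. Section 11.4.2 of the protocol requires data from both periods. SAP Section 6.1.3 specifies the full analysis set without repeating that condition, so a one-period subject might stay in the model, but would still supply no paired difference.

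**What to change.** Reconcile Sections 6.6, 7.2 and 9.3 with Tables 15-2 and 16-1:

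- In 7.2, replace the two general references with the specific rows for which the sponsor intends mandatory discontinuation, and make clear whether these bullets sit under the adverse-event heading.
- Bring the discontinuation wording of 9.3 into line with 7.2, and cite the definition table and the action table consistently.
- Make the interruption wording in 9.3 and the 4 rows agree with 6.6 and with the missed-dose bullet of 7.2, and say whether deferring Period 2 within the wash-out counts as an interruption.

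Which action applies to which row is for the sponsor's medical team to decide.

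The cost is a wording amendment or clarification, with no new assessments and no change to the analysis model. Because the SAP reports that the trial was terminated early, the immediate use is to record in the study report how any liver or renal alerts were handled between periods, and to correct the text before it is reused.
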